Study population: Initially our goal is to enroll 60 T1D subjects (50% male) with the goal of completing 40 in the adult cohort. Ultimately, if the study drug is tolerated and safe in our adult cohort, we plan to amend the protocol to include adolescents, with involvement of [name], the co-PI on the JDRF award. With the addition of the adolescent cohort, we plan to recruit 133 T1D subjects with the goal of completing 80. Submission of this amendment will occur in late year 1 ONLY IF there is no concerning safety signal in the adult cohort. Inclusion criteria: (1) T1D of >9 months duration based on a clinical course consistent with T1D and rapid conversion to insulin requirement after diagnosis (2) HbA1c 6.5-10% (adults) or any HbA1c up to 12% (pediatrics) and (3) age 12-60 years of age. Exclusion criteria include (1) any comorbid condition associated with inflammation, IR, or dyslipidemia including cancer (with the exception of skin cancer), heart failure, active or end stage liver disease, end stage kidney disease, inadequately treated thyroid disease, or rheumatologic disease; (2) tobacco or marijuana use; (3) pregnancy; (4) regular or frequent oral steroid use; (5) current use of insulin sensitizing medications, neuroleptics or ergot-related medications, or triptan medications for migraine, (6) diagnosis or history of psychosis and (7) diabetes of other cause such as MODY or cystic fibrosis-related diabetes. BMI will not be restricted in order to allow secondary analysis for effects of BMI on responsiveness to BCQR. Postmenarchal premenopausal females will be tested in the early follicular phase (cycle d2-10) where possible.

C. Study Design and Research Methods

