Investigational product: Bromocriptine Quick Release (Cycloset™): Bromocriptine itself has been available and widely used for Parkinson's disease and prolactinoma for decades. It was also used for a time for congestive heart failure. BCQR is FDA approved for adult and T2D is currently undergoing safety and efficacy trials in T2D adolescents. BCQR has a similar side effect profile to standard formulations of bromocriptine. Common side effects include mild hypotension, mild fatigue/somnolence, headache, depressed mood, insomnia, nausea, and diarrhea. Less common and more serious side effects have been seen with BCQR including hypersensitivity reactions, hypoglycemia and syncope. Bromocriptine is

standardly used in young children, adolescents, and adults of all ages with hyperprolactinemia at higher doses than proposed in our study and should be well tolerated. To assess the hypotensive side effect of Bromocriptine, blood pressure measurements, as outlined by the CDC to access orthostatic hypotension, will be collected at every study visit for the adolescent cohort only. Continuous glucose monitoring and contact with study staff will help avoid hypo- or hyperglycemia. Potential benefits include improved glycemic control and decreased insulin requirement, as well as metabolic and vascular benefits related to decreased chronic SNS activity, decreased renin angiotensin system activation, and resetting of the circadian rhythm.

Study design: Eligible subjects will be randomized to order of treatment (placebo followed by BCQR vs. BCQR followed by placebo). Belmar Pharmacy will be supplying the study drug (BCQR 0.8 mg and identical placebo tablets). The study timeline for Phase 1 is illustrated in **Fig 6**. Phase 2 consists of visits identical to Phase 1 numbered 5-7.

Visit 1: Screening visit:

Prescreening will be done by phone or in conjunction with a clinical diabetes visit. The full screening visit will include the consent process, history, physical exam, and screening labs (HbA1c, comprehensive

Figure 6: Study timeline (for each medication phase)

[figure not shown]
Stage day: 0

14

~21

~26

~28

metabolic panel, TSH (adult participants only), urine microalbumin, lipids). All females will also have a pregnancy test and detailed menstrual history. Adult females will have FSH and estradiol to determine pre- or postmenopausal status.

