Optional combined Visit 1, 2, and 3: For subjects that might have long distances to travel or scheduling conflicts, a combined visit will be provided as an option. For adolescents, a point of care A1c will be completed at screening to satisfy inclusion/exclusion criteria in addition to the other procedures outlined under visit 1. If participant is eligible and enrolled, IDS pharmacy will dispense medication to the study team. The sleep and insulin diaries along with the Activwatch will be given to the subject at Visit 1 or 2. A phone call from the study doctor will be made to the subject during week 3 of the

phase to review CGM data as well as discuss any issues that may have come up. Subjects will also be reminded at this time to complete the insulin and sleep diaries and wear the Actiwatch during the last week.

Visit 4: Mixed Meal Tolerance Test (MMTT) Visit: Subjects will present in the AM fasting following the 1-day study diet. Fasting Dynapulse measurements of vascular stiffness and central and peripheral blood pressure, EndoPAT measurements of endothelial function and augmentation index, and measurement of heart rate variability for autonomic tone will be performed. An IV will then be placed and baseline labs will be drawn, including hormonal and metabolic markers (described in MMTT detailed methods below). Additional blood will be drawn and stored for future vascular and inflammatory markers. Next, an MMTT will be performed as described below. Pills will be counted to assess compliance, and the hypoglycemic and sleep questionnaires will be repeated. An optional MRI will be performed of the chest and abdomen.

After at least a four week washout period, the full cycle will be repeated with the second blinded intervention, starting with Visit 5 (medication start visit as above, but without DEXA). Measurements following the placebo phase will serve as the untreated baseline.

Optional combined visits 5, 6 and 7 (adolescents only): For subjects that might have long distances to travel or scheduling conflicts a combined visit will be provided as an option. Activity watch, questionnaires, CGM and study medication will be mailed to participant following the 4-week washout period. In the event a participant does not feel comfortable placing CGM at home, they will be able to come to the CTRC for CGM placement assistance.

Methods:

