Mixed Meal Tolerance Test⁷⁵: A standardized mixed meal (Boost +®, 45 grams of carbohydrate) meal tolerance test (MMTT) will take place at the end of each medication cycle as in our previous studies⁶¹. The subject will be confirmed to have arrived fasting, caffeine-free, and having taken the AM dose of the study medication. Daily insulin pump basal rate or basal long acting insulin injections should continue as usual. The subject will be instructed not to exercise throughout the MMTT. A point of care fasting glucose will be done prior to the MMTT. The MMTT may be cancelled and rescheduled at the investigator's discretion if this blood glucose measurement is below 50 mg/dl or above 300 mg/dl. An intravenous catheter (IV) will be inserted for multiple blood draws. At approximately -30 minutes, a fasting blood draw will occur, including the timed labs below, plus a fasting lipid panel, HbA1c, adiponectin, and progesterone (female only to document state of menstrual cycle). A urine sample will be collected for urine microalbumin:Cr ratio. At approximately -5 minutes, the "time 0" blood draw will occur. Immediately after the blood draw, the subject will subcutaneously inject a standard bolus of their usual short-acting mealtime insulin with their standard correction factor (CF) and carbohydrate:insulin ratio for ingestion of the liquid meal containing 45 grams of carbohydrate, 14 grams of fat, and 14 grams of protein. The phase 2 MMTT will be completed with the same bolus dose as the phase 1 MMTT unless the starting blood glucose requires a different CF dose. Immediately after bolusing with insulin, as close to the true "time 0" as possible, and to be completed within 5 minutes, the participant will drink the meal (Boost +®). Actual blood draw times will be recorded, as well as insulin dose and all glucose measurements taken throughout the MMTT. During the MMTT, blood is drawn for glucose, insulin, C-peptide, triglycerides, NEFA, GLP-1, glucagon levels at -30(approximately), 0, 30, 60, 120, 180 and 240 minutes and serum creatinine and cystatin C (adolescents only). If a subject experiences a hypoglycemic event or any other event compromising safety, the MMTT will be stopped at investigator discretion.

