Study Diet: There is a small risk that blood sugars will be higher or lower than normal at home while eating the study diet as it may differ from the subject's usual diet. To avoid this risk, subjects will be asked to monitor their blood sugars at least four times a day while on the study diets and following procedures. Carbohydrate content will also be provided for each food item to assist with carbohydrate counting.

Continuous Glucose Monitoring (CGM): A continuous glucose sensor will be placed (Dexcom G4 Platinum, Dexcom, Inc., San Diego, CA) to assess home blood glucose values. The sensor is well tolerated with the only side effects being mild to moderate site irritation in 2% of patients, and in rare cases, skin infection.

DEXA Scan: There is no pain with this procedure. For females, a urine pregnancy test will be checked prior to the test to avoid any x-ray exposure to a pregnant person. This procedure involves the use of X-rays. The amount of radiation exposure during the DEXA test is approximately 15 mSv which is 7 times the level of background radiation in Colorado or approximately equal to the amount of radiation a subject would receive being outdoors in Denver for two days.

Mixed meal tolerance test: There is a small risk that blood sugars will be higher or lower than normal at home while eating the study diet and with the mixed meal tolerance test (MMTT) as it may differ from the subject's usual diet. To avoid this risk, blood sugars will be checked before and after the meal and additional carbohydrate or insulin given as indicated.

Ansar Heart rate variability, Endopat and Dynapulse: There are no significant risks associated with these procedures. There may be slight discomfort when the blood pressure cuff is inflated.

MRI: The MRI is a non-invasive scan. MRI uses a magnet and there is no radiation and no risk involved with the MRI. The scan may be loud, therefore participants may be provided with audio protection and optional television. Metal cannot enter the MRI area. Participants will be screened to assure no metal is present prior to MRI.

Indirect Calorimetry: The subject may feel claustrophobic.

Waist Circumference: There is no risk associated with measuring waist circumference

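### No pregnancy test is specified in the visible text before the second drug course, so the last specified test is nominally at least 56 days old when phase 2 drug is dispensed or mailed

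*Combined protocol and SAP*

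**What the plan says.** Pregnancy is the third exclusion in section IV.B ("3) pregnancy; (4) regular or frequent oral steroid use"). The trial is a two-period cross-over: "Eligible subjects will be randomized to order of treatment (placebo followed by BCQR vs. BCQR followed by placebo"). Section IV.C gives four weeks on each treatment, separated by a washout of at least four weeks.

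Two pregnancy tests are written down.

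- At Visit 1 (screening): "All females will also have a pregnancy test and detailed menstrual history".
- Under DEXA Scan in section IV.D: "For females, a urine pregnancy test will be checked prior to the test to avoid any x-ray exposure to a pregnant person". The scan is done at Visit 2, the medication start visit.

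On the second period, section IV.C says "Phase 2 consists of visits identical to Phase 1 numbered 5-7". The end of the Visit 4 text describes the repeat cycle as "starting with Visit 5 (medication start visit as above, but without DEXA"). For adolescents who take the optional combined visits 5, 6 and 7: "Activity watch, questionnaires, CGM and study medication will be mailed to participant following the 4-week washout period".

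Some indirect information is also collected. Section IV.B asks that postmenarchal, premenopausal females be tested early in the cycle when feasible. The MMTT labs include "progesterone (female only to document state of menstrual cycle"). Assessment of Safety (IV.D) has adverse event and illness questions at every visit.

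The withdrawal criteria, given under BCQR intervention and again under Study stopping and subject discontinuation criteria (both IV.D), do not mention pregnancy.

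**The concern.** The only test attached to starting drug is there because of the X-ray. When Visit 5 drops the scan, the stated reason for that test goes with it, and the Visit 2 text lists no separate test that would carry over. A site following the visible schedule could start a second course of blinded drug in someone who by then meets the plan's own exclusion. For an adolescent who has the drug mailed, no in-person contact before the first phase 2 dose is described either.

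If a pregnancy did come to light during the study, the visible withdrawal criteria give staff no written instruction to stop study drug. What is at stake is participant safety and consistent use of an entry criterion. The estimate of treatment effect is not in question.

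**Working it through.** The plan states no figure on this point, so there is none to reproduce. The check has three parts.

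**1. Does a test carry over to Visit 5?**

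- Visits 5 to 7 mirror Visits 2 to 4. Screening (Visit 1) is not repeated, so the screening test is not repeated.
- The Visit 2 text lists the scan, CGM training, insulin and glucose records, questionnaires and dispensing. The only pregnancy test at that visit comes through the DEXA paragraph.
- Visit 5 expressly omits the scan. The statement that the visits are identical therefore cannot bring the test with it.
- The urine sample at the MMTT is for the microalbumin ratio, and the progesterone draw is for cycle stage. Neither is specified as a pregnancy test.

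**2. How old is the last specified test?** Take Visit 2 as day 0.

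- Phase 1 treatment: 4 × 7 = 28 days.
- Washout: at least 4 × 7 = 28 days.
- Age at Visit 5: 28 + 28 = 56 days or more.
- If the approximate day 26 label left from Figure 6 marked the end of phase 1, the result would be 26 + 28 = 54 days.
- By the end of phase 2: 3 × 28 = 84 days or more.
- With a test at Visit 5, the age would be about 0 days.

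**3. How many participants does this touch?** Inputs are the targets under Study population and Recruitment, with half of participants female.

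| Scenario | Basis | Females starting phase 2 |
|---|---|---|
| Both cohorts | 80 completers | 0.5 × 80 = 40 |
| Both cohorts | 100 eligible | 0.5 × 100 = 50 |
| Adults only | 40 completers | 0.5 × 40 = 20 |
| Adults only | 60 enrolled × 100/133 ≈ 45 eligible | 0.5 × 45.1 ≈ 23 |

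The last row assumes that the eligibility ratio for the full study applies to adults alone.

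Only those randomized to placebo first receive BCQR in phase 2. The allocation ratio is not stated. Assuming equal allocation, with both cohorts open, that is 0.5 × 40 = 20 to 0.5 × 50 = 25 females. If the placebo-first share were anywhere from 40% to 60%, the range would be 0.4 × 40 = 16 to 0.6 × 50 = 30.

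Half the full cohort is adolescent. If the sex split holds within that half, the mail option could reach at most 0.5 × 40 = 20 to 0.5 × 50 = 25 adolescent females, and that only if every one of them chose it.

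**The case against.** The strongest objection is that this is an absence claim made without the page most likely to settle it. Figure 6 is captioned as the timeline for each medication phase and could list procedures by visit. The consent pages could hold wording on testing and on stopping drug. This stands as a limit: the text supports saying that no test is specified in the visible sections, and no more. A reader might infer that the trial does not test for pregnancy in phase 2, but the documents do not show that.

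A second objection is that Visit 5 repeats no other entry criterion either, and that the documents give no reason for the pregnancy exclusion and describe no fetal risk. A reader might infer expected fetal harm, or a count of exposed pregnancies. Neither can be drawn from these documents. What remains is that the plan already repeats a pregnancy test after screening for the sake of one scan, while the visible text specifies none before a further four weeks of drug.

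Third, the indirect checks have some value. Aiming Visit 7 at the early part of the cycle means projecting the cycle when phase 2 is scheduled. With a cycle of about 28 days, an assumption, Visit 5 would also fall near that window. Adverse event questions are asked at each visit. So it would be wrong to treat all indirect information as dating from the phase 1 MMTT. But the scheduling is conditional on feasibility, and none of these checks is a pregnancy test.

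Finally, the head-counts are not numbers at risk. A reader might take half of all 60 enrolled adults, that is 30, as the adults-only bound. That uses enrolment where the two-cohort bound uses eligibility, so the two would not be comparable.

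**Conclusion.** The point holds for the visible text. No pregnancy test is specified between the Visit 2 scan and the release of phase 2 drug, a nominal gap of at least 56 days, and pregnancy found on study is not among the written reasons to stop drug. The plan's own exclusion is therefore not rechecked, on paper, before the second course.

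At most about 40 to 50 females are affected if both cohorts open, and about 20 to 23 if only adults enrol. These figures rest on the plan's recruitment targets, an even sex split and, for the 23, the borrowed eligibility ratio. Postmenopausal and premenarchal participants would reduce them by amounts the documents do not give, so the number actually at risk is unknown. No material effect on the primary analysis is claimed.

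This is a safety omission that should be corrected because correction is easy. It does not threaten the validity of the trial. Confidence is medium because of the unseen figure and consent pages.

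**What to change.** **Test.** In the Visit 5 text and the optional combined visits 5 to 7 text of section IV.C, require a negative urine pregnancy test in postmenarchal, premenopausal females before phase 2 drug is dispensed. Where drug is mailed, require it before release or before the first dose. Visit 2 needs no change, since the pre-scan test already falls there.

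**Stopping drug.** In both places in section IV.D that list withdrawal criteria, add pregnancy found on study as a separate reason to stop study drug. Three details matter:

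- Keep it out of the list of predefined serious adverse events.
- State that it does not count toward the rule that stops the trial when more than two subjects are affected.
- Keep safety follow-up for that participant, as an exception to the rule that withdrawn subjects provide no further data. Otherwise the change would end contact with the person it is meant to protect.

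If Figure 6 or the consent form already covers this, copy the wording into these sections.

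**Cost.** One urine test per eligible female, at most about 40 to 50, plus a few sentences. Because treatment is blinded, both sequences must be tested, so under equal allocation about half the tests precede placebo. Adolescents using the mail option need a kit or a clinic stop, at most about 20 to 25 of them. Each participant found pregnant before completing phase 2 loses her treatment-placebo pair for the paired comparison.

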A. Outcome Measure(s):

Primary outcome measures are mean CGM glucose and insulin dose (SA#1), impact of age and BMI on response to therapy (SA#2) and improvement in brachial artery distensibility and RH-PAT (SA#3). Insulin dose was chosen as a clinical primary outcome because of the short treatment duration and to allow insulin dose adjustments as needed to avoid hypoglycemia. Secondary outcomes (see detailed methods below) include measures of (1) glycemic control (CGM parameters (SD, %hyperglycemic)); (2) baseline/postprandial metabolic labs [area under the curve (AUC) for MMTT glucose, insulin, NEFA, triglycerides, glucagon, and glucagon-like peptide1 (GLP1); (3) hypoglycemia frequency and awareness (CGM %hypoglycemic, hypoglycemia symptoms scores (Gold method, Clarke method, and the McAuley score⁶⁴⁻⁶⁷); (4) SNS activity (heart rate variability); (5) other metabolic markers (HDL, LDL); (6) circadian rhythm/sleep effects (sleep quality scores, measured sleep with actiwatch sleep monitor); (7) CVD measures (arterial stiffness by Dynapulse, endothelial function by EndoPAT, and blood pressure), and (8), blood storage for future inflammatory (IL-6, TNF- α , hsCRP, adiponectin), and vascular (endothelin 1, PAI-1, ICAM, renin, angiotensin, aldosterone) markers.

B. Description of Population to be Enrolled:

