Visit 2: Medication Start Visit: Qualifying subjects will return for a medication start visit and DEXA scan for body composition and estimation of daily caloric needs. Subjects will be trained in the use of a CGM system (Dexcom G4 Platinum). The monitor will be in real time unblinded mode throughout the uptitration portion of each study phase for safety purposes by guarding against hypoglycemia due to insulin sensitization and allowing informed insulin dose adjustment with assistance from study personnel if needed. Baseline insulin dosing totals and average blood glucose will be recorded by subjects 3 days prior to starting the study medication. Subjects will also complete hypoglycemia and sleep questionnaires to assess frequency and awareness of lows, sleep patterns and sleep adequacy. Medication will be dispensed by the UCH or CHCO pharmacy to blind subjects and study personnel. Subjects will uptitrate study medication as follows: BCQR (0.8 mg) or placebo- 1 pill QAM for one week, then 2 pills QAM for one week, then 4 pills QAM for the remainder of the 4 weeks. If an uptitration step is not tolerated, subjects will be returned to the last tolerated dose for a few days and uptitration will be attempted again. If again not tolerated, subjects will remain at the last tolerated dose as long as this is at least 1.6 mg QAM. If unable to reach minimum acceptable dose, subjects will be withdrawn from the study.

Visit 3: Pre-MMTT Visit: Subjects will return for provision of Activwatch and review of CGM data from the past 3 weeks. There will be continued data collection regarding glycemic control, variability, frequency of hypoglycemia, physical activity, and sleep duration and quality. Detailed 7-day sleep and insulin diaries will again be provided for the last week. Prior to each post-medication metabolic study day, subjects will also be provided with a 1-day standardized, macronutrient-controlled, weight maintenance diet (45% carbohydrate, 20% protein, 35% fat) with caloric content based on prior DEXA lean body mass and an activity factor as in our previous studies. Depending on scheduling conflicts and the ability to pick up study diet, study staff may provide participants with food recommendations to eat 1 day prior to MMTT with the same macronutrient distribution listed above.

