Data handling: Data will be examined for completeness and errors during data cleaning, in order to remove any spurious or incorrect data and complete any missing data in the database where possible. Protocol deviations will be reported to COMIRB and the study Safety Officer within 30 days of the deviation. Deviations from the original statistical analysis plan will be reported to COMIRB with the next continuing review and disclosed in any publication resulting from this study.

Assessment of Safety: Safety parameters will include monitoring of any adverse events (AEs) or serious adverse events (SAEs), including number of hypoglycemic episodes and percentage of time spent hypoglycemic during the last week of CGM data. Safety parameters will be obtained by questionnaire at each visit, and will include reports of any AEs or SAEs.

At each visit, study subjects will be asked if they have had any AE, including illness, injury or hospitalization since the last visit. If so, the onset date, resolution date, severity and outcome will be recorded. All AEs will be reviewed by the PIs and a determination of SAE or AE status will be made. All SAEs will be reported to the IRB, safety officer, and sponsor following regulations. Bromocriptine is less well studied in adolescents and therefore further assessment of Bromocriptine's hypotensive effect will be monitored at each visit for adolescents aged 12-17 via orthostatic measurements. Assessment of intercurrent illnesses will be made by asking study participants of any illnesses or symptoms they have had since the prior visit, onset date and resolution date, severity and outcome of the illness. Subjects with SAEs will be followed until resolution of the event. All other subjects with AEs will be followed until the end of the study.

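### The stated CGM hypoglycaemia safety window is the last week of data, and no BCQR versus placebo comparison of CGM hypoglycaemia is prespecified to cover uptitration

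*Combined protocol and SAP*

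**What the plan says.** Assessment of Safety (section D) names as safety parameters the "number of hypoglycemic episodes and percentage of time spent hypoglycemic during the last week of CGM data". This is the only window attached to CGM hypoglycaemia anywhere in the document.

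Hypoglycaemia by CGM also appears in SA#1, as a secondary outcome in Outcome Measure(s) (IV.A), and as a secondary efficacy measure in Assessment of Efficacy (F). None of these gives a window. The Analysis Plan (F) compares metabolic parameters between placebo and treatment visits, so a treatment comparison is intended. The one other CGM window, the last 2 weeks of each phase, is stated for mean glucose only.

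The dosing schedule under Visit 2 is "1 pill QAM for one week, then 2 pills QAM for one week, then 4 pills QAM for the remainder of the 4 weeks". The sensor runs in "real time unblinded mode throughout the uptitration portion of each study phase for safety purposes by guarding against hypoglycemia due to insulin sensitization". Visit 3 includes "review of CGM data from the past 3 weeks". Where visits are combined, the study doctor telephones during week 3 of the "phase to review CGM data as well as discuss any issues that may have come up". At medication start, "Subjects will also complete hypoglycemia and sleep questionnaires to assess frequency and awareness of lows", and at Visit 4 "the hypoglycemic and sleep questionnaires will be repeated"; no recall period is given.

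**The concern.** The protocol itself treats uptitration as a period of hypoglycaemia risk, and BCQR had not been studied in T1D before. Yet the stated safety window begins a week after the nominal move to 4 pills.

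The documents give several reasons why the treatment difference might change over a phase:

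- Lows from insulin sensitization are anticipated during uptitration.
- Insulin dose was made a primary outcome partly "to allow insulin dose adjustments as needed to avoid hypoglycemia", so doses may already have been adapted by week 4.
- The nominal dose is highest in weeks 3 and 4.
- SA#1 expects BCQR to make subjects less susceptible to lows.

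A single late week cannot separate these. Subjects with T1D can have lows on placebo too, so only a comparison by treatment can show whether lows during uptitration are more frequent on BCQR. It matters also because Recruitment (C) singles out hypoglycaemia in the safety review that precedes adding adolescents.

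Leaving the % hypoglycemic window open also means that it could be chosen after the data have been seen.

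**Working it through.** The power section gives no figure for CGM hypoglycaemia, so there is none to reproduce. The check is a day count, followed by an illustration under assumed values.

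**Inputs.** Phase length is 4 weeks, or 28 days (Research Design and Methods). The pill schedule is under Visit 2 and the window under Assessment of Safety. Days are counted from day 0, as in Figure 6.

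**Overlap on the nominal schedule**
- 1 pill: days 0-6. 2 pills: days 7-13. 4 pills: days 14-27. Uptitration is therefore days 0-13, or 14 days.
- Last week: days 21-27. Days shared with uptitration: 0 of 14.
- Share of the phase used: 7/28 = 25%. The 21 days outside comprise all 14 uptitration days and 7 of the 14 days at 4 pills.
- If % hypoglycemic borrowed the mean-glucose window (days 14-27), the overlap would again be 0.

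**Sensitivity of the count.** Figure 6 marks the later visit days as approximate.

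| Last CGM day | Last week | Shared with days 0-13 | Last 2 weeks | Shared with days 0-13 |
|---|---|---|---|---|
| 25 | 19-25 | 0 | 12-25 | 2 |
| 26 | 20-26 | 0 | 13-26 | 1 |
| 27 | 21-27 | 0 | 14-27 | 0 |

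With data to day 27, the step to 4 pills must slip by 8 days (from day 14 to day 22) before one day is shared. Otherwise CGM data must end by day 19, when the last week is days 13-19.

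**Subject-days per treatment, assuming full wear.** For 40 completers: 40 × 7 = 280 of 40 × 28 = 1,120. For 80 completers: 80 × 7 = 560 of 80 × 28 = 2,240.

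**Possible size.** Let d be the mean BCQR minus placebo difference in percentage of time hypoglycaemic over weeks 1-3, and e the difference in week 4. With even wear, the whole-phase difference is (3d + e)/4. The last-week result minus the whole-phase result is then e − (3d + e)/4 = 0.75(e − d). The documents give neither d nor e, so the range is assumed:

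| e − d (points) | −2 | −1 | 0 | +1 | +2 |
|---|---|---|---|---|---|
| Last week minus whole phase (points) | −1.5 | −0.75 | 0 | +0.75 | +1.5 |

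One point is 0.01 × 1,440 = 14.4 minutes per day, so 1.5 points is 21.6 minutes per day.

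**Early withdrawal.** Suppose a subject's last CGM day is day 9. Read literally, that subject's last week of data is days 3-9: 4 days at 1 pill and 3 at 2 pills. A completer contributes 7 days at 4 pills. If the phrase means week 4, the subject contributes nothing to that phase. The text does not say which is meant.

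**The case against.** An end-of-phase window is a coherent choice. Insulin and sleep diaries cover the last week and mean glucose the last 2 weeks, so the design measures effect after titration, in what it calls a pilot. This stands as a reason to keep the last week, but it does not supply a comparison for the earlier weeks.

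The safety wording may be narrower than it looks. The list is not exhaustive, and the time limit may attach only to percentage of time, leaving episodes unrestricted. This also stands. On either reading, nothing is prespecified for uptitration.

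A reader might infer any of four stronger things, which the documents do not support:

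- *Early lows go unwatched.* They do not. There is real-time CGM, the week-3 review, adverse-event questioning with onset and resolution dates, and discontinuation criteria for assisted events that apply to the whole phase. Dated reports could even be tabulated by treatment and week, although no such analysis is planned.
- *No treatment comparison of hypoglycaemia is planned.* One is, in section F. It lacks only a window, so early weeks are neither included nor excluded.
- *The last week hides an excess of lows.* The table above is symmetric because nothing in the documents fixes a direction.
- *Early withdrawals are lost.* That follows only if the window is read as week 4. The Analysis Plan includes all randomized subjects.

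A whole-phase summary also has a weakness of its own: it mixes doses, particularly where a step was retried or a subject stopped early. A breakdown by week answers this only in part.

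**Conclusion.** The point holds as an analysis gap. Followed as written, the safety summary of at least percentage of time hypoglycaemic uses 25% of the phase and none of the nominal uptitration period. The planned secondary comparison does not fill the gap, because its window is undefined.

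The 0-day overlap assumes the nominal schedule and CGM data to about the end of the phase. Retried dose steps or early stopping can create overlap in individual subjects. The effect on a treatment estimate is unknown in size and sign; the ±1.5 points is an illustration, not a forecast. The point concerns CGM hypoglycaemia only, since the questionnaires may cover earlier weeks. No primary outcome is affected and subjects are not left without monitoring. The change is still worth making, because the sensor data are already being collected.

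**What to change.** In Assessment of Safety, add percentage of time hypoglycaemic and hypoglycaemic episodes per day of sensor wear, from day 0 to the end of the phase or withdrawal. Report both overall and by week (or uptitration versus remainder). Compare BCQR with placebo in all dosed subjects, as estimates with 95% confidence intervals adjusted for treatment order. Use methods suited to skewed percentages and counts: for example, a negative binomial mixed model with sensor days as offset for episodes, and a bootstrap by subject for percentage of time. Subjects with only one phase should be able to contribute.

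Keep the last week as the end-of-phase summary. Say whether it applies to both parameters and how it is defined for a subject who stops early. In Assessment of Efficacy, state the window for % hypoglycemic.

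The cost is wording in two sections, a longer CGM extract and a little more analysis. No procedure is added. Weekly summaries will mix doses where a step was retried, and whole-phase summaries will do so where a subject stopped early; the report should say so.
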